4 OBJECTIVES AND ENDPOINTS / OUTCOME MEASURES

4.1 Primary objective

The ARON trial will test the impact of a diagnostic algorithm including a standardised clinical assessment, a POC CRP test, and safety netting advice.

More specifically, our research question is whether this diagnostic algorithm is able to safely reduce antibiotic prescribing in acutely ill children presenting to ambulatory care.

The main aim of our study is to establish the assumed superiority of a **diagnostic algorithm** including a standardised clinical assessment, a POC CRP test and safety netting advice over usual care to reduce **antibiotic prescribing rates** (both immediate and delayed prescribing).

Null hypothesis: the diagnostic algorithm including a standardised clinical assessment, a POC CRP test and safety netting advice will not reduce the proportion of subjects receiving a prescription for immediate or delayed antibiotic treatment at the index consultation compared to usual care

Alternative hypothesis: the diagnostic algorithm including a standardised clinical assessment and a POC CRP test with EBM guided advice will reduce the proportion of subjects receiving a prescription for immediate or delayed antibiotic treatment at the index consultation compared to usual care

The primary outcome is antibiotic prescribing rate at index consultation (immediate or delayed) (day 0).

Any reduction in the use of antibiotics should be considered alongside any negative effect on the well-being of a child. Therefore, time until full clinical recovery, additional investigations, re-consultations and antibiotics prescribed during follow-up (secondary outcomes) should be considered alongside any potential reduction in antibiotic use (primary outcome).

- P Children aged 6 months to 12 years of age with an acute illness episode presenting to in-hours general practices or community paediatrics offices
- I Diagnostic algorithm including a standardised clinical assessment, a POC CRP test and safety netting advice
- C Diagnosis and treatment/management as per usual care
- O Antibiotic prescribing rate at index consultation (immediate or delayed)
- T This outcome will be registered **immediately** at the index consultation

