The non-inferiority limit for the above 4 secondary outcomes is 1 day, 3%, 4%, and 2%, respectively, i.e. the intervention will be deemed non-inferior if the difference between the allocated groups (intervention – control) is less

than 1 day, 3%, 4%, and 2%, respectively. Therefore, the intervention will be deemed non-inferior if the upper limit of the 95% confidence interval lies below 1 day, 3%, 4%, and 2%, respectively.

Sample size for comparison of 2 means (for the first secondary outcome: time to full clinical recovery) and 2 proportions (for the other three secondary outcomes) for a non-inferiority trial was calculated with the following assumptions:

- 1-β = 0.80
- Allocation ratio (intervention/usual care) = 1
- Design effect (DE) = 1 + ρ(n-1)
- n = number individuals per cluster
- ρ = intracluster correlation coefficient
- · We account for the clustering at the level of the individual physician
- n = 50 patients per cluster
- ρ = 0.025 (Previous studies have illustrated that in primary care ICCs for clinical outcomes are lower than those for process outcomes and the ICC for adverse effects to be around 0.025)(28)
- Resulting DE = 2.225
- to account for multiple testing (n=4), we have applied the Bonferroni-Holm correction, generally considered to be a rather conservative approach to control the family-wise error rate.(29) Therefore, our significance levels for the 4 secondary outcomes were 0.0125 (α /4), 0.167 (α /3), 0.025 (α /2), and 0.05 (α /4), respectively.

Secondary outcome		Preliminary sample size	Significance level (α)	Design effect (DE)	Total sample size (preliminary sample size * DE) for this outcome
1.	Time to clinical recovery (days)	575	0.0125	2.225	1280
2.	Additional investigations at index and/or during follow-up (%)	2079	0.0167	2.225	4626
3.	Re-consultations during follow-up (%)	2312	0.025	2.225	5144
4.	Antibiotic prescribing rate during follow up (%)	1906	0.05	2.225	4240

Taking into account the required sample size for these analyses of the primary study outcome and the secondary outcomes, aiming to recruit a **total sample size of 6111 patients** will be sufficient. Considering we previously recruited 8962 and 3981 acutely ill children in Belgium, this seems feasible.

11.1.2 impact of Covid on the primary outcome and revised sample size calculation during the trial

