Imputation techniques are not applicable in this dataset.

Statistical Methodology

Statistical Procedures

-

Baseline characteristics & Clinical features

Presentation of baseline characteristics of the study population and comparability of the two arms will be based on the following variables:

- Age (median and 25-75 percentiles)
- Gender (percentage)

Baseline characteristics and clinical features will be reported using frequencies and percentages, means and standard deviations or medians and interquartile ranges, and minimum / maximum, as appropriate.

Primary endpoint

For the analysis of the primary outcome, we will use a mixed-effects logistic regression analysis to account for the clustering at practice level. The child's age and study arm will be included as predefined covariates in the model. We will do this using R software using the 'glmer' function of the 'lme4' package. Results will be reported by an odds ratio (OR) with 95% confidence intervals.

Multiple imputation will be applied to deal with missing data. Ten complete datasets will be constructed and analysed. The 10 results will be combined into a final result following Rubin's rule.

We will analyse the primary endpoint according to the intention-to-treat (ITT) approach, given the pragmatic nature of our trial.

The participating physicians were asked to recruit children with an acute illness consecutively. GPs were likely to have breached the assumption of consecutive inclusions if they:

- recruited fewer than 10 patients per year;
- performed a POC CRP test on nearly all (>90%) of the included children; and/or
- included nearly exclusively children (>90%) based on a negative result on all three items of the clinical decision tree that do not need antibiotics and exclude those that might need antibiotic treatment.

Apart from the intention-to-treat analysis, a per protocol sensitivity analysis will be performed only considering physicians who have recruited children consecutively.

Secondary endpoint – Proportional measures

We will provide a descriptive analysis of the proportion of subjects with the outcome of interest for each randomization group.

A mixed-effects logistic regression model will be employed to address clustering at the practice level. The child's age and study arm will be included as predefined covariates in the model. Odds ratios, along with their corresponding 95% confidence intervals will be reported.

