Null hypothesis. The diagnostic algorithm including a standardized clinical assessment, a POC CRP test and safety netting advice is inferior to usual care in terms of the number of days until subjects reach full clinical recovery.

Analysis. We will conduct a descriptive analysis to determine the median time to recovery for each randomization group. IQR will also be provided for each group.

For graphical representation, Kaplan-Meier curves will be generated. These curves will be used in combination with a log-rank test to compare the survival curves of the randomization groups.

Additionally, will employ a mixed-effects Cox regression model to address clustering at the practice level. The child's age and study arm will be included as predefined covariates in the model. Hazard ratios, along with their corresponding 95% confidence intervals, will be reported.

Exploratory endpoints – Proportional measures

We will provide a descriptive analysis of the proportion of subjects with the outcome of interest for each randomization group.

A mixed-effects logistic regression model will be employed to address clustering at the practice level. The child's age and study arm will be included as predefined covariates in the model. Odds ratios, along with their corresponding 95% confidence intervals will be reported.

••

Exploratory endpoints – Satisfactory measures

Statistical analysis not applicable due to the qualitative nature of the data.

Upon transcription of the interviews verbatim, an inductive thematic analysis approach is employed to analyse the data. The entire data analysis process was facilitated using qualitative data analysis software QSR NVIVO software version 12 (QSR International Pty Ltd, Melbourne, Australia).

Findings will be centred on main themes and subthemes closely aligned with the research inquiries and reflective of the interview content. In addition, illustrative quotes will be included.

Exploratory endpoints - Cost-effectiveness of the intervention

Different types of economic evaluations will be conducted to compare participants in the intervention group with those in the control group:

- **Costing study** to comprehend the overall cost structure, identify significant cost drivers, and compare the cost impact.

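### The four secondary non-inferiority outcomes have a stated Holm correction but an unadjusted 95% CI rule, the SAP plans no estimate on the margin scale, and the re-consultation sample size does not follow from its printed inputs

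*Protocol*

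**What the plan says.** Protocol section 11.1.1 (secondary outcomes) sets non-inferiority margins of 1 day for time to recovery and 3, 4 and 2 percentage points for additional investigations, re-consultation and antibiotics during follow-up. Three statements there bear on how non-inferiority is decided.

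- Multiplicity: "we have applied the Bonferroni-Holm correction, generally considered to be a rather conservative approach to control the family-wise error rate".
- Levels: "our significance levels for the 4 secondary outcomes were 0.0125", and then, in list order, 0.167 (0.0167 in the table), 0.025 and 0.05. The last is labelled α/4. Sidedness is not stated.
- Decision: "the intervention will be deemed non-inferior if the upper limit of the 95% confidence interval lies below 1 day, 3%, 4%, and 2%, respectively".

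The sample size table gives the row "Re-consultations during follow-up" a preliminary size of 2312 and a total of 5144 after a design effect of 2.225. The section then concludes, "Taking into account the required sample size for these analyses of the primary study outcome and the secondary outcomes", that 6111 patients are sufficient. Section 11.1.2 later raises the target to 7000 because of the primary outcome.

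For the binary secondary outcomes the SAP plans the proportion in each arm and a mixed-effects logistic model: "Odds ratios, along with their corresponding 95% confidence intervals will be reported". For recovery it repeats the inferiority null in days, and plans medians with IQR, Kaplan-Meier curves, a log-rank test and a mixed-effects Cox model: "Hazard ratios, along with their corresponding 95% confidence intervals, will be reported". Table 2 of the SAP is to show odds ratios with a p-value for the treatment effect. The SAP text supplied contains no margin, no multiplicity step and no interval for a difference.

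**The concern.** Protocol section 4.1 asks that these four outcomes be weighed alongside any fall in antibiotic prescribing, so they carry the word safely in the research question. Three things stand in the way.

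1. The multiplicity claim and the decision rule are different procedures. Holm attaches its levels to the ordered p-values and stops at the first failure. The protocol attaches them to outcomes by list order when sizing, and then judges every outcome at one level.
2. The margins are absolute differences, while the planned model output is on ratio scales.
3. The re-consultation row, the largest of the four secondary sample sizes, does not follow from its own inputs.

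If this is left open, the procedure that decides non-inferiority can be chosen after the results are known.

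**Working it through.** **Inputs** (protocol 11.1.1): 80% power; 1:1 allocation; ICC 0.025 with 50 per cluster, so design effect 1 + 0.025 × 49 = 2.225. Rates, intervention vs usual care: investigations 9.0% vs 9.8%, margin 3%; re-consultation 33% vs 34%, margin 4%; antibiotics in follow-up 7% vs 8%, margin 2%. Recovery: means 4.06 vs 4.15 days, SD 3.89, margin 1 day.

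**Formula for proportions** (total N, unpooled variance, one-sided α):

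N = 2 × (z₁₋α + z₀.₈)² × [pI(1−pI) + pC(1−pC)] / (margin + pC − pI)²

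**Reproducing the plan's figures**

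| Row | α | Calculation | N | Stated |
|---|---|---|---|---|
| Investigations | 0.0167 | 2 × 8.814 × 0.1703 / 0.038² | 2079 | 2079 |
| Antibiotics in follow-up | 0.05 | 2 × 6.183 × 0.1387 / 0.03² | 1906 | 1906 |
| Re-consultation | 0.025 | 2 × 7.849 × 0.4455 / 0.05² | 2797 | 2312 |

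With two-sided levels, rows 2 and 4 give 2468 and 2419, so those two rows were sized one-sided. For recovery, 4 × (2.241 + 0.842)² × 3.89² / d² gives 575 (as stated) at one-sided 0.0125 only with d = 1, that is, a true difference of zero. With the printed 0.09-day benefit (d = 1.09) it gives 484 one-sided and 568 two-sided. Row 1 therefore does not settle sidedness.

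**Re-consultation.** 2797.3 × 2.225 = 6224, against 5144 printed; 2797/2312 = 1.21, or 21% more. The printed 2312 needs a denominator of 0.055² instead of 0.05². Either of two changes gives that:

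- a 4.5% margin: 2311.9, and × 2.225 = 5144;
- unrounded rates 1.5 points apart at the 4% margin, such as 32.75% vs 34.25%: 2311.5.

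The documents do not say which, if either, was used.

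**Power on the printed inputs** (one-sided 0.025): Φ(0.05/SE − 1.96), with SE = √[0.4455 / (N / (2 × DE))].

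| N | DE | 0.05/SE | Power |
|---|---|---|---|
| 6111 | 2.225 | 2.776 | 79.3% |
| 7000 | 2.225 | 2.971 | 84.4% |
| 7000 in 122 practices | 1 + 0.025 × (7000/122 − 1) = 2.409 | 2.855 | 81.5% |

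In 122 practices the required N is 2797.3 × 2.409 = about 6740.

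**Levels used to size and to judge.** One-sided 0.0125, 0.0167, 0.025 and 0.05 correspond to two-sided intervals of 97.5%, 96.7%, 95% and 90%. A two-sided 95% interval matches only the third. Outcome 4 is sized at one-sided 0.05 and would be judged at 0.025, for which it needs 2419.2 × 2.225 = 5383 rather than 4240 (× 2.409 = 5829). Both are below 7000.

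**Family-wise error of the flat rule**, with outcomes claimed singly and all four at their margins: two-sided 95% intervals, independent, 1 − 0.975⁴ = 9.6%. Simulation with equal correlations gives 7.8% at 0.5 and 5.7% at 0.8. If the limit is a one-sided 95% bound, 1 − 0.95⁴ = 18.5%. If all four must succeed there is no inflation.

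**Scale.** A 2-point margin on the assumed 8% is an odds ratio of (0.10/0.90)/(0.08/0.92) = 1.28. On an illustrative control rate of 4% it is 1.53, and on 12% it is 1.19. No fixed odds-ratio limit stands in for the stated margin, and a hazard ratio has no fixed equivalent in days.

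**The case against.** The strongest reply is that little turns on the arithmetic now. The 6111 belongs to the initial calculation. The operative 7000 covers 6224, and also the 6740 for 122 practices, and 79.3% is close to 80%. That stands. A reader might infer that the trial is underpowered for re-consultation or needs more children; the figures do not support this. Nor do they prove that a 4.5% margin was used, since unrounded rates give the same printed number.

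The Holm sentence appears in a list of sizing assumptions, so it may never have been meant as an analysis rule. This is fair, but the sentence says the method was used to control the family-wise error, and no analysis step delivers that.

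The 9.6% is a worst case. A reader might take it as the trial's actual error rate, but the documents do not say that outcomes will be claimed one by one, and correlation lowers it. Nor does it follow that applying Holm must bring re-consultation below 80% power. The table's levels imply a family level of one-sided 0.05. Simulated there with 7000 in 122 practices (correlations 0 and 0.5, complete data), power is 86–87%.

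Finally, the SAP does plan proportions by arm and medians, and it restates the null for recovery. A crude difference could be read off, but without a clustered interval, which is what the decision rule needs.

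**Conclusion.** The point holds in three parts.

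1. The protocol states Holm control, but decides by unadjusted 95% intervals and fixes its sizing levels by list order. The possible excess error is up to about 9.6% under the conditions given above, and none if all four outcomes must succeed.
2. In the SAP text supplied, no planned analysis yields the interval that the rule compares with the margins. This is the most consequential part, because the non-inferiority tests cannot be carried out as written. Part of the SAP was not available for review, so the absence is stated only for the text seen.
3. On the printed inputs the re-consultation row should read 2797 / 6224. Hence 6111 fell slightly short of the stated 80% power, at 79.3%, while 7000 gives 81.5% to 84%.

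The power figures assume the printed rates, an ICC of 0.025, equal practice sizes, complete data and one-sided 0.025. One-sided sizing is shown for rows 2 and 4 only.

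**What to change.** - **SAP:** add practice-clustered risk differences for the three binary outcomes and a mean difference in days for recovery, each with a confidence interval compared with the stated margin. The odds and hazard ratios can stay as supporting results.
- **Both documents:** state one decision procedure and its sidedness. Either apply Holm to the ordered non-inferiority p-values at a stated family level, or require all four outcomes to meet their margins and remove the Holm claim.
- **Outcome 4:** use the same level to size and to judge it.
- **Re-consultation row:** reconcile it with its inputs (2797 / 6224 if the printed inputs are right) and restate its power at 7000.
- **Misprints:** correct 0.167 to 0.0167, and the second α/4, attached to 0.05, to α.

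This costs wording and a small extra analysis of data already being collected, with no added patients. The downside is that, if all four must succeed, joint power is lower than the power for any single outcome.

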The S62005 ARON trial was planned before the COVID-19 pandemic. Though, the trial actually started in the initial part of the pandemic, just as the Delta variant (second wave) was first emerging: early 2021. The ARON trial kept going through all subsequent COVID-19 waves and is currently still ongoing.

The COVID-19 pandemic has shown that antibiotic prescribing has (for the better) declined during the pandemic, as shown by several studies and reports:

- https://www.ecdc.europa.eu/en/news-events/reported-decrease-antibiotic-consumption-across-eueea- during-covid-19-pandemic

KCE Trials programme

This has urged us to revise our sample size calculation, based on the overall prevalence found in the first patients recruited, given the start of our trial during the pandemic.

This amendement concerns a clarification of the impact the COVID-19 pandemic has had on recruitment as well as the overall prevalence of our primary outcome, the antibiotic prescribing rate in children.

AIMS

With this amendment, we aim to:

- (1) investigate the influence of the COVID-19 pandemic on antibiotic prescribing rates in practices included in the ARON trial and (2) redetermine the required sample size for the ARON trial.
- (3) monitor whether inclusions were done consecutively, as per the study protocol, in order to minimize selection bias.

METHODS

1. Audit of antibiotic prescribing rate before and during the COVID-19 pandemic

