Contact Datum Is kleiner dan of gelijk aan 31/10/2022 ARON 2.En de periode dat ze gerekruteerd hebben tijdens de trial (gemakkelijk te vinden in Redcap - bv 1 mei 2021 t/m 30 november 2022). b.Hoeveel kinderen hebben minstens 1 AB voorschrift gekregen						
Medicatie	BCFI boom	ls gelijk aan	Antibacteriële middelen			
Contact	Datum	ls kleiner dan of gelijk aan	31/10/2022			
Patiëntenadministratie	Geboortedatum	ls kleiner dan of gelijk aan	30/11/2020			
Contact	Datum	ls groter dan of gelijk aan	01/05/2021			
Medicatie	Datum	ls groter dan of gelijk aan	01/05/2021			
Patiëntenadministratie	Geboortedatum	ls groter dan of gelijk aan	01/05/2009			
Contact	Auteur	ls gelijk aan				
Contact	Туре	ls gelijk aan	Consultatie			
Medicatie	Datum	ls kleiner dan of gelijk aan	31/10/2022			

Figure 8. Audit questions (after start of the trial) in CareConnect software (Corilus).

Most software packages, e.g., CareConnect², Daktari³, HealthOne⁴, of which the former dominate the market, have a statistics/search module. This allows for easy and uniform access to the required data.

2. Sample size calculation

The original sample size calculation was based on previous data, assuming an overall prescribing rate of 26.5% in those children recruited for our trial.

The overall prevalence was found to be 18% overall in children recruited in the first 4938 patients recruited in the ARON trial.

If we were to assume a reduction of 5.3% (proportionate to our original reduction) between the usual care group and the intervention group, using a 5% significance level (alpha 0.05), an intracluster correlation coefficient (ICC) of 0.063 (based on data from the ERNIE2 study in the exact same population), and power of 90% (beta 0.1), this would require **63 clusters of 50 patients** in both arms, resulting in **6300 children**.

R code:

We used the n4props-function in the R package CRTSize, using the following command:

n4props(0.2065,0.1435,50,0.063, alpha = 0.05, power=0.9, AR=1, two.tailed=TRUE, digits=3)

Considering the pragmatic nature of this trial and in correspondence with the 10% of practices performing nonconsecutive inclusion of patients (high risk of selection bias) during the ERNIE2 trial, we will perform sensitivity analyses only considering physicians who have recruited in a consecutive way. Taking into account the required sample size for this analysis of the primary study outcome, these assumptions result in a total sample size of 7000 patients for the primary study outcome.

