- multicentre: six academic centres for primary care will be involved in the recruitment of 122 primary care practices
- pragmatic: criteria excluding patients from participation will be limited as well as procedures that do not reflect care as usual
- cluster: randomization occurs at the level of the primary care practice while patients are the unit of analysis
- randomized: block randomization per academic centre will be performed to assign primary care practices to either the intervention or the control arm
- controlled: the intervention will be compared with usual care
- superiority: the trial is designed to show that the intervention is superior to usual care

Randomization

In order to avoid contamination between physicians working in the same practice, randomization will happen at the level of the physician's practice.

General practice clinics and community paediatric centres will be randomized in one of the two study arms in a 1:1 ratio using a block randomization system stratified per recruiting academic centre in order to guarantee that allocation to either the usual care or the intervention arm is balanced within every region.

Stratified block randomization will be done using an electronic random numbers generator in blocks of four practices. Randomization and concealment will be centralized at the KU Leuven and conducted by a staff member not involved in data collection or delivering the intervention.

Sample size calculation

The original sample size calculation in the approved protocol version 2.0 was based on previous data from the ERNIE2 trial, assuming an overall antibiotic prescribing proportion of 26.5% in those children recruited for our trial.

The overall antibiotic proportion was found to be 18% in the first 4938 patients recruited in the ARON trial.

If we were to assume a reduction of 5.3% (proportionate to our original reduction) between the usual care group and the intervention group, using a 5% significance level (alpha 0.05), an intracluster correlation coefficient (ICC) of 0.063 (based on data from the ERNIE2 trial in the exact same population), and power of 90% (beta 0.1), this would require 63 clusters of 50 patients in both arms, resulting in 6300 children.

R code:

We used the n4props-function in the R package CRTSize, using the following command: n4props(pc = 0.2065, pe = 0.1435, m = 50, ICC = 0.063, alpha = 0.05, power=0.9, AR=1, two.tailed=TRUE, digits=3).

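### The mid-trial sample size revision takes the prescribing rate from 4938 of the trial's own children but leaves the ICC of 0.063 and the cluster size of 50 unchecked against the same records

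*Protocol*

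**What the plan says.** Protocol 11.1.2 says that prescribing fell during the pandemic, and continues: "This has urged us to revise our sample size calculation, based on the overall prevalence found in the first patients recruited". Its sample size subsection recalls that the trial was planned "assuming an overall prescribing rate of 26.5% in those children recruited for our trial" and reports the new figure: "The overall prevalence was found to be 18% overall in children recruited in the first 4938 patients recruited in the ARON trial". The target difference is rescaled as well: "If we were to assume a reduction of 5.3% (proportionate to our original reduction) between the usual care group and the intervention group".

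The clustering input is not re-estimated. The revision uses "an intracluster correlation coefficient (ICC) of 0.063 (based on data from the ERNIE2 study in the exact same population", which is the value and source given in Protocol 11.1.1 for the calculation made before the trial. The command is "n4props(0.2065,0.1435,50,0.063, alpha = 0.05, power=0.9, AR=1, two.tailed=TRUE, digits=3", so the cluster size also stays at 50. The result is 63 clusters of 50 per arm, 6300 children, raised to 7000 to allow for 10% of practices recruiting non-consecutively.

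The SAP section on sample size repeats all of this ("The overall antibiotic proportion was found to be 18% in the first 4938 patients recruited in the ARON trial", then the same ICC and command). Neither document reports an ICC or cluster sizes from the recruited children, plans to estimate them at the revision, or shows how the result depends on them.

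**The concern.** A cluster-trial sample size rests on two nuisance parameters, the event rate and the ICC. The revision was prompted by evidence that the ERNIE2-based rate did not fit the recruited children. It updates that parameter and keeps the other from the same outside source, on the ground that the population is exactly the same.

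For a binary outcome the ICC is tied to the rate. Carrying 0.063 from 26.5% to 18% is therefore itself an assumption about how much practices differ, and the plan does not state it. The design effect is about 4, so the ICC moves the required size strongly. The 4938 children come from randomised practices, so the data that gave the 18% can also give an ICC and the real cluster sizes, without separating the arms. Until that is done, nobody can say whether 6300 or 7000 is generous or short for the stated 90% power.

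**Working it through.** **Inputs** (Protocol 11.1.2 and SAP, sample size calculation): pc = 0.2065, pe = 0.1435, m = 50, ICC = 0.063, two-sided alpha 0.05, power 0.90, 1:1 allocation.

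**Reproducing the plan.** Clusters per arm: k = (z0.975 + z0.90)² × [pc(1−pc) + pe(1−pe)] × [1 + (m−1)ICC] / [m(pc−pe)²].
- (1.960 + 1.282)² = 10.507
- Variance term: 0.16386 + 0.12291 = 0.28677
- Design effect: 1 + 49 × 0.063 = 4.087
- Denominator: 50 × 0.063² = 0.19845 (here 0.063 is the difference in rates, which happens to equal the ICC)
- k = 10.507 × 0.28677 × 4.087 / 0.19845 = 62.06, rounded up to 63 per arm, or 6300 children. 6300 / 0.9 = 7000.

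This matches the plan. The initial inputs (0.3043 and 0.2265) give k = 54.90, so 55 per arm and 5500 children, which also matches.

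**Sensitivity to the ICC.** Power = Φ(|pc−pe| / √(variance term × design effect / (k·m)) − 1.96). ICC values other than 0.063 are assumptions; the documents give none from the recruited children.

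| ICC | Children needed for 90% | Power, 63 clusters of 50 per arm | Power, 70 clusters of 50 per arm |
|---|---|---|---|
| 0.03 | 3800 | 98.7% | 99.3% |
| 0.04 | 4500 | 97.0% | 98.1% |
| 0.05 | 5300 | 94.5% | 96.3% |
| 0.063 | 6300 | 90.4% | 93.1% |
| 0.07 | 6800 | 88.0% | 91.1% |
| 0.08 | 7500 | 84.5% | 88.1% |
| 0.10 | 9000 | 77.6% | 81.7% |

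Solving for the ICC at which power is exactly 90% gives 0.0643 at 63 clusters per arm and 0.0737 at 70.

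**What the fall in rate alone implies.** Take a random-intercept logistic model for practice, as planned for the primary analysis, and integrate over a normal intercept. An ICC of 0.063 at 26.5% corresponds to a practice SD of 0.597 on the logit scale; the same SD at 18% gives an ICC of 0.050. Calibrating at the original control rate of 30.43% gives SD 0.576 and ICC 0.047 at 18%. These need k = 52.7 and 50.2, so 5300 and 5100 children. For the ICC to remain 0.063 at 18%, the SD would have to be 0.673.

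**Can the trial's records answer the question?** The number of practices behind the 4938 children is not stated. Assuming 80 to 122 equal-sized practices and a true ICC of 0.063, the standard error of the estimate is √{2(1−ICC)²[1+(m−1)ICC]² / [m(m−1)(K−1)]}, with K practices and m = 4938/K. This gives 0.0118 (K = 80) to 0.0105 (K = 122). Ignoring arm adds about (d/2)² / (0.18 × 0.82) to the ICC: 0.0048 for d = 5.3 points and 0.0067 for d = 6.3 points.

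**Cluster size.** The plan has 122 practices, 61 per arm, against the 63 calculated. With 7000/122 = 57.4 children each, power at ICC 0.063 is still about 90.4% for the command's rates. Observed, unequal sizes are not considered.

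**The effect size in the same lines.** The text states 5.3 points; the command has 0.2065 − 0.1435 = 6.3 points, with a mean of 17.5%. The pair 0.2065 and 0.1535 gives 5.3 points, a mean of 18%, and a relative reduction of 25.7%, close to the original 0.0778/0.3043 = 25.6%. The command implies 30.5%. At 5.3 points and ICC 0.063, k = 89.8, so 9000 children; power is 77.5% with 63 clusters per arm and 81.6% with 70. At ICC 0.05 it is 84.0% and 87.6%.

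**The case against.** Taking an ICC from a named earlier trial with the same type of outcome is ordinary planning practice, and 6300 follows exactly from the stated inputs. Describing the population as the same may refer to patients and setting; a lower prescribing rate does not by itself refute it, and ERNIE2 cannot be inspected here. Both points stand, and they are why the phrase needs qualifying rather than being called false.

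A reader might infer more: that the fall to 18% has made 0.063 obsolete, or that the trial is underpowered because of it. The documents do not support either. The only consequence that can be derived from the fall in rate, under a constant practice SD, is a lower ICC, which makes 6300 conservative. The low-power rows of the table rest on assumed ICCs, and no passage says that practices came to differ more.

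It can also be said that the estimate may not settle the matter. With a standard error near 0.011, an estimate close to 0.063 would have limits of roughly 0.043 to 0.083, or about 4800 to 7700 children, which spans the current target. That is fair, but a range anchored in the trial's own data is still better than one unchecked value with no range.

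Finally, this concerns planning only. The primary mixed model estimates practice variation from the final data, so its confidence interval does not use 0.063. That stands in full.

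**Conclusion.** The point holds in a limited form. The revision re-estimates the rate and rescales the difference, but carries over the ICC and the cluster size without checking them against records that could inform both. The stated 90% power has almost no margin at 63 clusters per arm (the limit is an ICC of about 0.064) and a modest margin if 7000 children means 70 clusters of 50 per arm (about 0.074). The true value could lie on either side: about 0.047 to 0.050 under a constant logit-scale SD, higher if practice variation widened.

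All these limits use the command's 6.3 points and equal clusters of 50. If the stated 5.3 points is what is meant, the limits fall to about 0.038 and 0.045, so the two figures must be reconciled before any restated power can be relied on. The consequence is for the credibility of the stated size and power, and so for how a null or imprecise result is read. It does not touch the validity of the primary analysis.

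**What to change.** In Protocol 11.1.2 and the SAP section on sample size:

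1. Estimate the ICC with 95% limits from the pooled 4938 records without using arm (random-intercept model or ANOVA estimator), and report the number of practices and the observed cluster sizes. Note the slight upward bias of about 0.005 to 0.007 from ignoring arm.
2. Reconcile the stated 5.3-point reduction with the 6.3 points in the command.
3. Rerun n4props with the reconciled rates, the estimated ICC and its limits, and a realistic cluster size. Restate the required size and the power of 7000 children over that range.
4. Qualify the statement that the ICC comes from exactly the same population, for example by saying that it was taken from ERNIE2 before the pandemic and giving the trial's own estimate beside it.

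The cost is one extra model on data the trial holds, and some wording. It needs no unblinding, spends no alpha and requires no extra patients. The restated power may be less favourable than 90%. If recruitment has already ended, steps 1 to 4 still apply as a statement of assumptions and sensitivity.
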